#### **I. Abstract**

Suicide has become the second leading cause of death in children and teens in the United States. Since 2008, firearm suicide rates have increased by more than 89% making it the #2 cause of completed suicide in children. During this period of time, the Emergency Department (ED) has been thrust into the forefront of suicide prevention; there has been a 329% increase among patients presenting to the pediatric emergency department (PED) for self-harm behavior since 2007. Pediatric Emergency Medicine providers have a unique opportunity to intervene, counseling both caregivers and patients at risk for self-harm. Counseling in the medical setting is an effective means for creating behavior changes to improve patient safety, especially when families are given tangible resources/safety products. Eighty percent of firearms used in childhood suicides are owned by family members. Fortunately, safe storage of these firearms greatly decreases the likelihood of firearm-related death among children and adolescents. The purpose of this study is to measure change of firearm storage practices in families after receiving either targeted ED-based safety counseling or counseling with a safe firearm storage product. Patients presenting to the PED with a chief complaint of "Psychiatric Evaluation", including those presenting for suicidal ideation, aggression, and depression, will be included. Patients who do not have access to a home firearm, or who don't present with a caregiver will be excluded. Patients will be randomized to one of two study arms (1) a control arm receiving targeted firearm safety counseling or (2) an intervention arm receiving targeted firearm safety counseling in addition to the provision of two firearm cable locks. Information obtained from families will include caregiver demographics, age and number of children in the home, and current storage practices of firearms and medication. Follow up phone surveys at 4 weeks post ED visit will describe self-reported storage practices, other subsequent ED visits, and satisfaction with the ED encounter for both groups.

#### **II. Purpose of Study**

The primary purpose of this study is to determine if distribution of informational resources (such as handouts) coupled with distribution of firearm safety locks, improves self-reported securement of all firearms with locking devices (ie. cable lock, lockbox, gun safe) over informational resources alone. Secondary objectives include: reporting how families view ED-based firearm safety counseling and describing relative improvement among other lethal means safety measures: (1) firearms stored unloaded (2) firearms acquired/removed from the home, (3) medications stored with locking device and (4) medications removed from the home. Our study will focus on families of children presenting for psychiatric evaluation in a pediatric emergency department. We hypothesize that families that receive informational resources and firearm locks will report all firearms stored with a locking device 25% more frequently than families who receive informational resources alone.

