#### **III. Background**

Suicide is now the second leading cause of death in children and teens in the United States. This is of particular importance to PED providers because there has been a 2.5 fold increase in the number of suicide-related visits among adolescents over the last several years. In 2008 there were 529 firearm-related suicides in children compared to 1,003 in 2018. Access to firearms has been shown to be a key risk factor for completed suicide. Although a small minority of pediatric suicide attempts involve the use of a firearm, they are used in approximately 40% of all completed suicides, making firearms the second leading cause of completed suicide in children and adolescents. This is due to the fact that suicide attempts with firearms results in much higher rates of mortality, with greater than 90% of attempts ending in death. Among pediatric suicides in the US, over 80% of guns used in suicide attempts belong to a family member, with the majority involving handguns. Fortunately, this risk can be greatly mitigated with the safe storage of firearms, by as much as 78%. The AAP defines safe storage as firearms kept locked, unloaded with ammunition secured and stored separately. However, less than 40% of gun-owning families follow the AAP's safe storage guidelines leaving approximately 4.6 million American children living in households with at least one loaded, unlocked firearm.

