#### **IV. Study Design**

This will be a prospective, non-blinded, randomized controlled study in a Pediatric Emergency Department to determine the effect of gun lock distribution with informational resources on firearm storage practices compared to informational resources alone. The study cohort includes parents or legal guardian(s) of patients presenting to the Cincinnati Children’s Hospital Emergency Department for psychiatric evaluations who have any guns in their home. Parent or guardian of the patient must be present for enrollment. Informed consent will be obtained for those families agreeing to participate in the study. Parent/guardian will be asked if they are willing to complete a survey at time of encounter and again in 4 weeks from initial encounter. If they are unable to read, the survey will be read to them by the CRC. Families will be randomized, via block randomization, into one of two study arms: (1) a control arm receiving targeted firearm safety informational resources or (2) an intervention arm, receiving targeted firearm safety informational resources in addition to the provision of 2 cable-style firearm locks. Lethal means counseling (which includes discussion about locking hazardous items such as medications and firearms) is part of the standard safety planning that occurs when PIRC counsels families. All patients will still receive standard of care counseling by PIRC team members. The informational resources provided will include more specific information and advice related to firearm safety, discussing topics such as the four pillars of safe storage and the decreased risk of suicide when firearms are stored safely. Primary outcome is change in self-reported securement of **all** firearms with a locking device. Initial survey to be given before targeted information is provided. Follow up surveys at 4-6 weeks after the ED visit will determine self-reported storage practices of firearms and medications after receiving the intervention, and Likert-scale based satisfaction with pediatric ED encounter. Follow-up attempts will be attempted via text or phone. The surveys will be available in English only. The surveys will contain only the minimum PHI needed to allow for follow-up. Survey will be electronic with responses recorded via REDCap.

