## **IX. Data Analysis/Methods**

Data will be collected in REDCap and stored on a password protected computer available only to PI and co-investigators. Frequency of responses will be calculated at the completion of data collection. Analysis will be performed by the study team at CCHMC. Primary outcome is change in self-reported securement of **all** firearms with a locking device. This will be elucidated by comparing responses to the pre and post intervention surveys. Frequencies will be compared between the two study arms. For our secondary outcomes, questions regarding degree of satisfaction (which will be assessed via Likert scale), removal/acquisition of firearms, and (if applicable) use of provided gun locks. Based on prior studies that compared counseling to receipt of tangible resource, we can expect a 25% difference between

the groups. We will need 138 participants to detect a difference of this magnitude. Assuming a dropout rate of 30% a sample size of 200 will be necessary. The most recent CCHMC PIRC data show that 40-100 patient-families each month have reported gun ownership (This number is 100-150 pre-COVID). A Chi Squared test will be used to determine significance difference of proportions between the two groups. Limitations of our study include self-reporting of ownership and storage. This may be further limited as families who do not store weapon safely may be less likely to report ownership.

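### Is the trial sized for a different 25% effect from the one in its hypothesis?

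*Combined protocol and SAP*

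**What the plan says.** Section II (Purpose of Study) hypothesises that families given locks as well as information will "report all firearms stored with a locking device 25% more frequently than families who receive informational resources alone".

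Section IX (Data Analysis/Methods) relies on earlier work comparing counselling with a tangible resource and says "we can expect a 25% difference between" the groups. It continues: "We will need 138 participants to detect a difference of this magnitude". It then allows for attrition: "Assuming a dropout rate of 30% a sample size of 200 will be necessary". The analysis is named as follows: "A Chi Squared test will be used to determine significance difference of proportions between the two groups".

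The document does not give a control-arm proportion, significance level, sidedness, power or allocation ratio. Section IV (Study Design) says only "Families will be randomized, via block randomization, into one of two study arms". The one storage rate in the document is in Section III (Background): "less than 40% of gun-owning families follow the AAP's safe storage guidelines". It uses a stricter definition (locked, unloaded, ammunition secured separately) than the trial's outcome.

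**The concern.** A rate that is 25% higher is, read literally, a relative increase: from 40% to 50%, for example. A 25% difference between groups naturally reads as absolute: from 40% to 65%. These are very different targets for the same trial, and with no control rate, alpha or power in the text, a reader cannot recover which one the authors used.

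If the relative reading were the real hypothesis, the trial would be far too small at most control rates. A null result could then be taken as evidence against an effect that the study had little chance of finding.

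**Working it through.** **Inputs.** From Section IX: 138 evaluable, 30% dropout, 200 enrolled, a chi-squared test of two proportions, and an effect of 25%. Assumed because not stated: two-sided alpha of 0.05 (z = 1.960) and 1:1 allocation, so 138/2 = 69 per arm. The control rate p1 is varied.

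**Formulas.** With p2 the lock-arm rate, d = p2 − p1 and p̄ = (p1 + p2)/2:

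- n per arm = [1.960·√(2p̄(1−p̄)) + z_power·√(p1(1−p1) + p2(1−p2))]² / d²
- with continuity correction, n' = (n/4)·[1 + √(1 + 4/(n·d))]²
- power at m per arm = Φ{[d·√m − 1.960·√(2p̄(1−p̄))] / √(p1(1−p1) + p2(1−p2))}

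**Step 1: the plan's own figures, read as 25 points.**

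- 30% against 55%, 85% power, no correction: [1.370 + 1.036 × 0.676]² / 0.0625 = 68.6, so 69 per arm and 138 in total.
- 32% against 57%, 80% power: n = 60.8, and n' = 68.6 with continuity correction, so again 69 per arm and 138 in total.
- For control rates of 26% to 49%, the corrected calculation at 80% power gives totals of 134 to 140. The uncorrected one at 85% power gives 134 to 142.
- Dropout: 138/0.70 = 197, rounded to 200. In reverse, 200 × 0.70 = 140, which covers 138.

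So 138 is an ordinary answer for an absolute 25 points, and 200 follows from it. Which variant the authors used cannot be told from the text.

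**Step 2: power of 69 per arm on each reading (no correction).** For control 40%:

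- absolute, 40% to 65%: (0.25 × √69 − 1.384)/0.684 = 1.01, so power is 84%
- relative, 40% to 50%: (0.10 × √69 − 1.379)/0.700 = −0.78, so power is 22%

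| Control rate | Power, +25 points | Power, ratio 1.25 | Total N for 80% power, ratio 1.25 |
|---|---|---|---|
| 30% | 85% | 15% | 1246 |
| 40% | 84% | 22% | 776 |
| 50% | 87% | 31% | 494 |
| 60% | 92% | 47% | 304 |
| 70% | 98% | 71% | 170 |
| 73% | not possible to 2 points short of 100% | 81% | 136 |

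The last row's absolute target would be 98%, outside the range checked. Across control rates of 10% to 70% the absolute column never falls below 84%; with continuity correction the minimum is about 80%.

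**Step 3: does 138 rule out the relative reading?** Not strictly. At a ratio of 1.25, 136 are needed at a control rate of 73% (uncorrected) or 75% (corrected), both at 80% power. That would mean about 73% of control families with every firearm locked, against 91% with locks (1.25 × 73% = 91.25%). No stated control rate excludes this, though nothing in the document supports it.

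**Step 4: which effect does the sample-size sentence refer to?** In Section IX the magnitude to be detected is the one in the sentence immediately before, the difference between groups. The test named is for a difference of proportions. Section IX is therefore consistent within itself and does not depend on the wording in Section II.

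**The case for a change.** The strongest case for a change is that the hypothesis is what a null result is judged against, and its literal wording is relative. At a control rate of 40%, a true rise to 50% would be missed almost four times in five. Even with all 200 participants evaluable (100 per arm), the formula gives only 29% power there. Section II also speaks of relative improvement for its secondary measures, so context does not force the absolute reading. Two sentences would remove the doubt and cost no patients.

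The arithmetic stands, and so does the point that neither section names its scale. The inference that the plan must change does not. The low-power figures describe a design that the plan probably never intended, since Section IX gives the same 25% as a difference and a sample size that suits it. Writing in a control rate and power now would be back-fitting: 85% power uncorrected and 80% corrected explain 138 equally well. Nor does the wording govern how a result is interpreted. Section IX compares frequencies between arms, and from two observed proportions a reader can compute both the difference and the ratio.

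A further question is whether the 25% applies to a follow-up proportion or to the change obtained under "This will be elucidated by comparing responses to the pre and post intervention surveys". That concerns the definition of the primary outcome. It stands apart from the scale of the effect and lends this point no weight.

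**Conclusion.** The concern does not call for a change. Section II is loosely worded and the scale of the 25% is left unstated, but no number in the plan is shown to be wrong. Assuming a two-sided 5% test and 1:1 allocation, 138 evaluable participants give at least 84% power for 25 percentage points over control rates of 10% to 70% (about 80% at worst with continuity correction), and the step to 200 is sound. The shortfall, 22% power at a control rate of 40% and 31% at 50%, arises only if the Section II phrase is taken literally as a ratio. Section IX gives no support for that reading, and 138 would suit it only at a control rate of about 73% or more. Rewording would leave enrolment, the test and the results unchanged, so this is a slip of phrasing that an analyst reading Section IX would resolve without help.

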#### **III. Background**

Suicide is now the second leading cause of death in children and teens in the United States. This is of particular importance to PED providers because there has been a 2.5 fold increase in the number of suicide-related visits among adolescents over the last several years. In 2008 there were 529 firearm-related suicides in children compared to 1,003 in 2018. Access to firearms has been shown to be a key risk factor for completed suicide. Although a small minority of pediatric suicide attempts involve the use of a firearm, they are used in approximately 40% of all completed suicides, making firearms the second leading cause of completed suicide in children and adolescents. This is due to the fact that suicide attempts with firearms results in much higher rates of mortality, with greater than 90% of attempts ending in death. Among pediatric suicides in the US, over 80% of guns used in suicide attempts belong to a family member, with the majority involving handguns. Fortunately, this risk can be greatly mitigated with the safe storage of firearms, by as much as 78%. The AAP defines safe storage as firearms kept locked, unloaded with ammunition secured and stored separately. However, less than 40% of gun-owning families follow the AAP's safe storage guidelines leaving approximately 4.6 million American children living in households with at least one loaded, unlocked firearm.

Several studies have demonstrated the ability of medical providers to positively impact behaviors affecting patient safety. Pediatric Emergency Medicine providers have a unique opportunity to provide education to patients and families about firearm safety by providing targeted interventions during “teachable moments”. One Pediatric ED in Colorado instituted a curriculum for counseling families of children with suicidal ideation which improved storage of medications and firearms after counseling received in an Emergency Department. Not only did the majority of families hold favorable impressions of the counseling, but there was a 66% and 37% increase in safe storage of medication and firearms, respectively. Furthermore studies have demonstrated that when families receive tangible resources, they are more apt to have the desired change in behavior. There have, as yet, been no randomized controlled studies assessing the effectiveness of distribution of various resources on safe firearm storage in the PED setting.

#### **IV. Study Design**

This will be a prospective, non-blinded, randomized controlled study in a Pediatric Emergency Department to determine the effect of gun lock distribution with informational resources on firearm storage practices compared to informational resources alone. The study cohort includes parents or legal guardian(s) of patients presenting to the Cincinnati Children’s Hospital Emergency Department for psychiatric evaluations who have any guns in their home. Parent or guardian of the patient must be present for enrollment. Informed consent will be obtained for those families agreeing to participate in the study. Parent/guardian will be asked if they are willing to complete a survey at time of encounter and again in 4 weeks from initial encounter. If they are unable to read, the survey will be read to them by the CRC. Families will be randomized, via block randomization, into one of two study arms: (1) a control arm receiving targeted firearm safety informational resources or (2) an intervention arm, receiving targeted firearm safety informational resources in addition to the provision of 2 cable-style firearm locks. Lethal means counseling (which includes discussion about locking hazardous items such as medications and firearms) is part of the standard safety planning that occurs when PIRC counsels families. All patients will still receive standard of care counseling by PIRC team members. The informational resources provided will include more specific information and advice related to firearm safety, discussing topics such as the four pillars of safe storage and the decreased risk of suicide when firearms are stored safely. Primary outcome is change in self-reported securement of **all** firearms with a locking device. Initial survey to be given before targeted information is provided. Follow up surveys at 4-6 weeks after the ED visit will determine self-reported storage practices of firearms and medications after receiving the intervention, and Likert-scale based satisfaction with pediatric ED encounter. Follow-up attempts will be attempted via text or phone. The surveys will be available in English only. The surveys will contain only the minimum PHI needed to allow for follow-up. Survey will be electronic with responses recorded via REDCap.

#### **V. Duration**

The study will take approximately 1.5 years. Approximately 3 months will be dedicated to development of survey and script for research coordinators. Three months will be allotted for obtaining lockboxes and firearm safety education for CRCs. Assuming a 65% acquiescence this should take approximately 8 months to achieve the desired sample size based on limitations of enrollment by CRCs and PI. Follow-up phone surveys to describe firearm storage will occur at approximately 4 weeks from encounter. Data analysis and manuscript preparation will take approximately 4 months to complete.

#### **VI. Selection & Recruitment of Participants**

The study participants include parents or legal guardian(s) of children who present to the Cincinnati Children’s Base Campus Emergency Department ED for a Psychiatric Evaluation. Parents or legal guardian(s) of patients who meet the following eligibility criteria will be screened. A minimum amount of child’s information (i.e. age, gender) will be used to determine eligibility of parents and this information will not be retained at CCHMC for the purpose of this research study.

Inclusion criteria include parent or legal guardians of patients for chief complaint of psychiatric evaluation (including other complaints such as “behavior problem”, “aggression”, etc) who are:

- English-speaking
- Screen positive for firearm possession (in at least one location the patient spends time)

Parent/legal guardian must be present for survey and distribution of firearm cable locking device(s). Disposition of patient (admit vs discharge) will not affect inclusion.

- Exclusion criteria include:

- Guardian does not speak English
- If patient behavior in the ED leads to an otherwise unsafe environment
- Guardian not present for duration of encounter
- Guardian unwilling/unable to answer follow-up questions

In order to provide follow-up phone calls/texts patient identification will need to be obtained. There are no other populations that will be subject to undue influence. Participants will be recruited and screened for eligibility to this study while in the Emergency Department. Participants will only be contacted via phone number provided.

## **VII. Process of Obtaining Consent**

We will be seeking a waiver of documented consent for this study. Our study presents no more than minimal risk of harm or procedures that would normally require written consent. Our study is simply an expansion of the current standard of care counseling provided by PIRC, which written consent is not normally required for outside of the research context. The research staff will explain the study and present a study summary sheet to parent/caregiver (study participants). Participants will have the opportunity to ask questions prior to deciding whether to continue with enrollment or to decline. Assent will not be obtained because HIPAA identifiers from the child's medical record will not be used or retained at CCHMC.

### **Waiver of Consent and HIPAA Authorization for Screening Purposes**

We are requesting a waiver of consent and HIPAA authorization to screen for patient eligibility using electronic medical records. Identifiable data about eligible and ineligible (i.e. missed eligible) patients such as MRN, encounter ID, date/time of visit, provider name, demographics, relevant clinical data, inclusion/exclusion criteria, etc. will be collected in a secure database hosted by CCHMC and used for assessing study operational needs. Access to the screening log is only available to Cincinnati Children's Emergency Department research staff. No research will be conducted from the data collected in the database; it is only used for research oversight. Consent would not be possible for patients because of the nature of presentation to the ED. It is possible that some patients will have arrived when no study staff is available. The rights and welfare of patients will not be affected by the data collection and they will still receive the same care regardless of study participation.

